2.4.1.3 Supportive analyses

To support parametric analysis approach described in the Section 2.4.1.2, a one-sided 0.05 level Wilcoxon sign rank test or other statistical method based will be performed on the adjusted differences. The adjusted differences for the test product will be calculated in the following way

-

Adjusted differences of the test product at 3 hour on day 5 = Within subject change from baseline of 3 hour on day 5 - 0.25.

The result will be produced in the Table ([Table 14.2.2.1](#)).

Frequency and percentage of subjects with clinically relevant irritation responses will be provided by treatment. Clinically relevant irritation response for an individual subject is defined as, increase score in dryness from baseline of 1 or more with treatment ([Table 14.2.1.1](#) and [14.2.1.2](#)).

2.4.2 Secondary dermal response variables

The secondary efficacy variables are defined in the following sub-sections.

2.4.2.1 Secondary dermal response variable 1

The first secondary efficacy variable is examiner assessment of redness (Lukacovic, 1987) as per Appendix 2 of the protocol at day 5, 3 hour post last wash procedure.

2.4.2.2 Secondary dermal response variable 2

- The secondary efficacy variables are the examiner assessment of dryness and redness (Lukacovic, 1987) as per Appendix 2 of the protocol at day 2, 3 4 and 5, 3 hour post last wash procedure.
- Also a secondary efficacy variable is TEWL measurements on day 5, 3 hours post last wash procedure.
- Also a secondary efficacy variable is Corneometer measurements on day 5, 3 hours post last wash procedure.

2.4.3 Handling of missing values/censoring/discontinuations

Missing data will not be replaced or imputed. Dropouts will be included in analyses up to the point of discontinuation. Sensitivity analyses may be conducted if substantial number of subjects have discontinued from the study.

2.5 Analysis of secondary objectives

2.5.1 Dermal Response (secondary)

The first secondary endpoint will be tested for the non-inferiority of the test product to water in change from baseline on day 5 in examiner rating of redness.

| | | | |
|------------------|--|---------------------|----------------------|
| Document Name | gsk-207619-reporting-and-analysis-plan.pdf | | |
| Type | Version | Document Identifier | Effective Date |
| eldo_controlled | 1.0; CURRENT; Most-Recent; Effective | 090032d580e0a875 | 06-Apr-2018 06:53:51 |
| Reason For Issue | Auto Issue | | |

GSK Consumer Healthcare

Confidential

Page 20

Statistical Analysis Plan

207619

To test the above mentioned hypotheses an Analysis of Covariance Variance (ANOVA) (ANCOVA) model will be used. The change from baseline in examiner rating of redness to 3 hours following last wash procedure on day 5 will be considered as the response variable. The model will include treatment and site as fixed effects; ~~baseline examiner rating of redness as a covariate~~ and subject as a random effect.

Least Square Means (LSMeans) for each treatment will be presented. The treatment difference estimates (test product to water), upper one-sided 90% confidence limit will be presented. If the upper one-sided 90% confidence limit is less than 0.25 it will be concluded that the test product is not inferior to the water in the examiner rating of redness ([Table 14.2.2.3](#)).

Second, secondary endpoint examiner assessment of dryness ([Table 14.2.2.4](#)) and redness ([Table 14.2.2.5](#)) at day 2,3,4, and 5, 3 hour post last wash procedure will be analyzed using ANCOVA ANOVA model for both dryness and redness separately. The model will be same as mentioned for the primary and first secondary efficacy endpoint analyses. Adjusted means, 95% CI and p-values will be provided for the following treatment comparison.

- Positive Control versus water
- Positive Control versus test product
- Water versus un-washed area

Change from baseline in TEWL ([Table 14.2.3.1](#)) measurement and Corneometer measurement ([Table 14.2.3.2](#)) will be analysed using the ANCOVA model with treatment and site as fixed effect; baseline corresponding measurements as a covariate and subject as a random effect. The adjusted means, treatment differences, 95% CI and p-values will be presented for the following comparisons.

- Test product versus water
- Positive Control versus water
- Positive Control versus test product
- Water versus un-washed area

If data are sufficiently non-normal in distribution, the non-parametric Wilcoxon signed ranks test or appropriate alternative will be used with median differences and 95% confidence interval presented based on the Hodges-Lehmann method.

No adjustment will be made for multiplicity testing for the secondary endpoints; however consistency of effects will be taken into consideration in interpreting the results.

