## 5.2. Application Schedule

Each subject will have four test sites; two test sites (3x3 cm) marked out on each volar forearm (Figure 1, Section 3.4). The distance between different application sites must be at least 1 cm to prevent either the test product, positive control (Imperial Leather bar soap) or negative control (sterile water) wash from spreading over and influencing neighbouring test sites. The site on each forearm for each wash application (or unwashed) will be determined according to the provided randomisation schedule. The randomisation schedule will identify the test sites for the test product, positive control and water (negative control) wash applications, and the unwashed site.

A trained technician will wash each marked site with the appropriate product.

All wash procedures will be performed at the study site by a technician to ensure consistent wash application and correct product usage.

During the study, subjects will have the wash procedure completed four times daily at each allocated site, two wash applications in the morning (AM) and two wash applications in the afternoon (PM) on Days 1, 2, 3 and 4. On Day 5, subjects will have the wash procedure completed twice in the morning (AM) only. Each AM and PM wash procedure will be separated by a minimum of 3 hours.

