### 5.3.1 Randomisation

A unique screening number will identify each subject screened for study participation. Screening numbers will be assigned in ascending numerical order as each subject signs their consent form. Subjects who meet all inclusion and exclusion criteria will be randomized according to the randomisation schedule, which will be prepared to achieve balance between each forearm and upper and lower forearm. Randomisation numbers will be assigned in ascending numerical order as each subject is determined to be fully eligible.

The study site will receive two versions of the randomisation schedule, each in a sealed envelope and clearly marked as either “For Dispensing” or “Emergency Use Only”. The “For Dispensing” schedule will contain the list of randomisation numbers and the test site location (1 to 4) a letter code A, B, C or D will be used to determine which product is to be applied to which site.

The ‘Emergency Use Only’ randomisation schedule will only be removed from the sealed envelope in an emergency situation. This schedule will have a randomisation number followed by the letter. The schedule will have a footnote with a key for the letters identifying the treatments.

However, to maintain the blinding of the study as much as possible, all treatment allocations for all randomisation numbers on this randomisation schedule will be masked with scratch-off panels. Only the panels required for the unblinding the particular subject should be removed

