### 6.2.2. Corneometry

Corneometry is a standard measurement of skin moisturisation which uses an electrical capacitance method to model the water content of the skin (Eisner, *et al*, 1994). Corneometer measurements are included to provide support for examiner assessments. Corneometry will be initially measured at Baseline visit (Visit 2) prior to any study product application on both volar forearms at each designated test site. It will then be measured at the final visit (Day 5 - PM), at least 3 hours following the final wash procedure completed at that AM visit.

CCI

[figure not shown]
[figure not shown]

Document Name	GSK20170100107013		
Type	Version	Document Identifier	Effective Date
elido_clinicallabelcbc	1.0; CURRENT; Most-Recent; Effective	090032d580d0a8784	06-Mar-2018 07:52:18
Reason For Issue	Auto Issue		

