### 6.2.3. Transepidermal Water Loss (TEWL)

TEWL is a non-invasive method to measure the integrity of stratum corneum barrier function. This measurement has been included to provide support for the examiner assessments. TEWL will be initially measured at the Baseline visit (Visit 2) prior to any study product application on both forearms at all the designated sites. It will then be measured again at the final visit (Day 5 – PM), at least 3 hours following the final wash procedure completed at that AM visit.

CCI

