### 9.3.3. Secondary Analysis(es)

The non-inferiority analyses performed for primary endpoint will also be performed for the secondary endpoint based on examiner rating of redness on Day 5.

For secondary endpoints based on examiner rating of dryness and redness on Day 5 to compare positive control versus water, the same ANCOVA model as above will be used and the treatment difference (positive control to water), p-value and 95% confidence interval will be presented. Also for information, the treatment difference (positive control to test product) and treatment difference (water to unwashed), p-value, and 95% confidence interval will be presented.

For the other secondary endpoints of redness and dryness each day, TEWL and corneometer, the change from baseline will be analysed using ANCOVA with subject (random effect), treatment and site as factors with baseline value as a covariate. LSMeans for each treatment will be presented. The treatment differences (test product to water and positive control to water), p-value and 95% confidence intervals will be presented. Also for information, the treatment difference (positive control to test product) and treatment difference (water to unwashed), p-value, and 95% confidence interval will be presented.

If data are sufficiently non-normal in distribution, the non-parametric Wilcoxon signed ranks test will be used with median differences and 95% confidence interval presented based on the Hodges-Lehmann method.

Redness and dryness scores, TEWL and corneometer measurements at each time point and change from baseline in these scores and measurements at each time point will also summarized for test product, water, positive control and unwashed site using descriptive statistics such as the number of non-missing observations, mean, standard deviation, median, minimum, and maximum.

Document Name	GSK20170101Protocol001		
Type	Version	Document Identifier	Effective Date
elido_clinicalelbc	1.0; CURRENT; Most-Recent; Effective	090032d580d0a8784	06-Mar-2018 07:52:18
Reason For Issue	Auto Issue		

No adjustment will be made for multiplicity testing for the secondary endpoints, however consistency of effects will be taken into consideration in interpreting the results.

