2.8 Sample size calculation

The primary hypothesis is that the test product is not inferior to water in the change from baseline in the examiner rating of dryness on Day 5. Assuming that the standard deviation of the within subject treatment difference in change from baseline in examiner rating of dryness is 0.25 (based on previous study GSKCH: [CCI](#)

[REDACTED]

[REDACTED]

[REDACTED]

A sufficient number of subjects will be screened in order to randomise 45 subjects and to ensure that at least 40 subjects complete the study.

3 Changes to the Protocol Defined Statistical Analysis Plan

~~There were no changes or deviations to the originally planned statistical analysis specified in the [protocol version 1.0](#)~~ The use of the Wilcoxon type test in support of the primary was removed due to limitations of that approach. Any potential supportive analysis will be considered if the ANOVA assumptions are strained. [protocol version 1.0](#) [(Dated: 06/MAR/2017)].

| | | | |
|------------------|--|---------------------|----------------------|
| Document Name | gsk-207619-reporting-and-analysis-plan.pdf | | |
| Type | Version | Document Identifier | Effective Date |
| eldo_controlled | 1.0; CURRENT; Most-Recent; Effective | 090032d580e0a875 | 06-Apr-2018 06:53:51 |
| Reason For Issue | Auto Issue | | |

4 Appendix 1:

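### TEWL and corneometer model: a single slope on the raw site baseline blends between- and within-subject slopes and can lose some precision compared with a split baseline

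*SAP*

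**What the plan says.** Protocol 5.2 sets the layout: "Each subject will have four test sites; two test sites (3x3 cm) marked out on each volar forearm". Under Protocol 5.3 each subject carries all four conditions (test product, bar soap, water, unwashed), and the schedule in 5.3.1 is one "which will be prepared to achieve balance between each forearm and upper and lower forearm".

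Both instruments are read at baseline on every site. Protocol 6.2.2 has corneometry measured "prior to any study product application on both volar forearms at each designated test site", and 6.2.3 has TEWL measured "prior to any study product application on both forearms at all the designated sites". So each subject contributes four baseline values per instrument.

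In SAP 2.5.1 the response for the first instrument is "Change from baseline in TEWL", and corneometry is handled alike. The model has treatment and site as fixed effects, with "baseline corresponding measurements as a covariate and subject as a random effect". Protocol 9.3.3 describes the same model, with random subject, "treatment and site as factors with baseline value as a covariate". Neither document separates the baseline into a subject part and a site part. The SAP amendment dropped the baseline covariate for dryness and redness, where eligibility forces every baseline to zero. It kept the covariate for TEWL and corneometer, where baselines do vary.

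**The concern.** A site baseline has two parts: the subject's general level, and the amount by which that site differs from the subject's other sites. These parts need not predict Day 5 equally well. A subject's general level may persist almost fully, while a site's deviation may be largely reading error and regress strongly.

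Test product versus water and soap versus water are contrasts between sites of the same subject, so the general level cancels. Only the slope on the deviation helps. A random-intercept model with one raw covariate estimates a compromise between the two slopes, so chance differences between sites at baseline are not removed as efficiently as the data allow. What is at stake is the width of the intervals for the instrumental endpoints that support the examiner scores.

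**Working it through.** **Plan's own figure.** There is none for the precision of these two outcomes. The plan to "randomise 45 subjects and to ensure that at least 40 subjects complete the study" was set on dryness non-inferiority, and part of that calculation is redacted. It does not bear on this point.

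**Inputs.** From the documents: four sites per subject, all four conditions within subject, allocation balanced over position, 45 randomised and at least 40 completing. Assumed, because the documents give nothing for either instrument: the subject share of baseline variance (0.5 to 0.85), the within-subject slope of Day 5 on baseline (0 to 0.95) and the subject-level slope (0.4 to 0.95).

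**Formula.** Let β be the true within-subject slope of Day 5 on baseline, b the slope the model actually applies, σ²d the within-subject variance of baseline, and σ²e the within-subject residual variance at slope β. On the change scale every slope is lower by 1, so differences between slopes are unaffected. The variance of a treatment difference, relative to using β, is

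R = 1 + (b − β)² σ²d / σ²e, and the interval-width ratio is √R.

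If within-subject spread is the same at baseline and Day 5, then σ²e = (1 − β²)σ²d and R = 1 + (b − β)²/(1 − β²). Leaving the covariate out of a change analysis means b = 1, so its variance relative to the split model is 1 + (1 − β)²/(1 − β²) = 2/(1 + β).

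**Formula against simulation.** 40 subjects × 4 sites, balanced allocation, REML, 250 runs per setting. The rows shown have a subject share of 0.85.

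| β | Subject-level slope | Fitted b | R | √R | Simulated width, raw/split | Simulated width, raw/no covariate |
|---|---|---|---|---|---|---|
| 0 | 0.8 | 0.282 | 1 + 0.0795/1 = 1.080 | 1.039 | 1.037 | 0.739 |
| 0.2 | 0.8 | 0.422 | 1 + 0.0493/0.96 = 1.051 | 1.025 | 1.024 | 0.796 |
| 0.2 | 0.95 | 0.647 | 1 + 0.1998/0.96 = 1.208 | 1.099 | 1.095 | 0.854 |
| 0.4 | 0.8 | 0.550 | 1 + 0.0225/0.84 = 1.027 | 1.013 | 1.012 | 0.849 |
| 0.8 | 0.8 | 0.799 | 1.000 | 1.000 | 0.999 | 0.951 |

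The fitted slope lies between the two true slopes when they differ, and the loss vanishes when they agree. The last column also follows from the formula. In the third row, √(1.208 × 1.2/2) = √0.725 = 0.851, against 0.854 simulated.

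**A noisier case.** 45 subjects × 4 sites, with SDs of 2 (subject), 0.5 (subject change), 0.5 (stable site) and 1 (reading error).

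- σ²d = 0.25 + 1 = 1.25 and β = 0.25/1.25 = 0.2, which is −0.80 on the change scale.
- The fitted single slope on that scale was −0.37.
- σ²e = 1.25 × 0.96 = 1.20, so R = 1 + 0.43² × 1.25/1.20 = 1.19 and √R = 1.09.
- Simulation gave a variance ratio of 1.20 and intervals 9.5% wider.

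**Range.** Over all 24 settings of the first simulation, the raw/split width ratio ran from 0.999 to 1.095 and was at most about 1.04 in 22 of them. Against no covariate it was 0.73 to 0.99. There was no bias beyond simulation error, and coverage was 93 to 97%. Further runs at 45 × 4 gave standard-error ratios of 1.005 to 1.068 in ten of eleven settings, and 1.19 in the one with extreme between-subject spread. A separate set of twelve settings gave intervals 0.7% to 22% wider.

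**The case against.** Random-subject ANCOVA with the site baseline as covariate is conventional and valid. Protocol and SAP agree on it, and it can be programmed as written. TEWL and corneometry are supportive secondary outcomes with no margin, success rule or power target, and they are read for consistency without multiplicity control. The size of any loss depends on reading reliability and subject spread, which the documents do not give. On that view, splitting the covariate is a matter of preference. All of this stands, and it limits the point to an optional gain in precision.

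A reader might infer three stronger things. The documents do not support them.

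- *That the covariate brings no benefit.* It narrowed the interval by 1 to 27% against unadjusted change in all 24 settings of the first simulation. The loss is only relative to a split baseline.
- *That imperfect correction of site baselines biases the comparison.* Treatments are randomised to sites within subject with balance over position, so the slope applied affects variance, not expectation.
- *That the plan typically wastes several subjects.* A variance ratio of 1.10 to 1.20 would equal 45 × (1 − 1/1.10) = 4.1 to 45 × (1 − 1/1.20) = 7.5 subjects. That is the upper part of a range driven by assumption, and in many plausible settings the ratio is close to 1.

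What the objection does not answer is that the site-level readings are already collected, and a split baseline lost no appreciable precision in any setting tried.

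**Conclusion.** The point holds as a minor refinement. A single raw-baseline slope with a random subject blends two slopes of which only one is useful for within-subject comparisons. Under the assumed variances the cost is roughly 0 to 10% in interval width: near zero when the between- and within-subject slopes agree, and about 20% only with very large between-subject spread. These figures rest on assumed variance components, since the documents state no SD, correlation or reliability for either instrument. The planned analysis remains unbiased with sound coverage, and it is better than using no covariate. Dryness and redness are untouched, because their models no longer carry a baseline.

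**What to change.** In SAP 2.5.1, for Tables 14.2.3.1 and 14.2.3.2 only, replace the single baseline covariate by two: the subject's mean baseline over the four sites, and the site's baseline minus that mean. Keep treatment and site fixed and subject random. State that the mean uses all four Day 1 readings. Fitting subject as a fixed effect for these two outcomes gives the same within-subject adjustment. The split is preferable because it keeps the random-subject structure, and so the standard errors of the LSMeans, as planned.

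Record the change in SAP Section 3, since Protocol 9.3.3 names a single baseline covariate, and make it before unblinding. The template footnote for these outcomes needs editing anyway: it is keyed to Tables 14.2.2.5 and 6, names redness as the response and does not mention the random subject term.

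The cost is one SAP sentence, one derived variable and one degree of freedom. No new data are needed.

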2.5.2 Safety

2.5.2.1 Adverse events and Serious Adverse Events

All adverse events (AEs) will be listed in the ([Listing 16.2.7.1](#)) for the randomised subjects and all adverse events for the non-randomised subjects will be listed in [Listing 16.2.7.2](#).

| | | | |
|------------------|--|---------------------|----------------------|
| Document Name | gsk-207619-reporting-and-analysis-plan.pdf | | |
| Type | Version | Document Identifier | Effective Date |
| eldo_controlled | 1.0; CURRENT; Most-Recent; Effective | 090032d580e0a875 | 06-Apr-2018 06:53:51 |
| Reason For Issue | Auto Issue | | |

Treatment emergent adverse events (TEAEs) will be summarized by the number and percentage of subjects having any adverse event, an adverse event in each System Organ Class, and each individual adverse event ([Table 14.3.1.1](#)). All TEAEs will also be tabulated by severity and treatment ([Table 14.3.1.2](#)). Treatment-emergent AEs suspected of a relationship to study medication and those causing study discontinuation will be presented in a similar manner ([Table 14.3.1.3](#)). For treatment-related AEs, these will also be presented by severity and treatment, if applicable ([Table 14.3.1.4](#)).

Non-fatal serious adverse events and adverse events causing study treatment discontinuation will be listed ([Listing 14.3.2.1](#)).

2.6 Analysis of other variables

Not applicable.

2.7 Interim analysis

No interim analysis is planned.

2.8 Sample size calculation

The primary hypothesis is that the test product is not inferior to water in the change from baseline in the examiner rating of dryness on Day 5. Assuming that the standard deviation of the within subject treatment difference in change from baseline in examiner rating of dryness is 0.25 (based on previous study GSKCH: [CCI](#)

[REDACTED]

[REDACTED]

[REDACTED]

A sufficient number of subjects will be screened in order to randomise 45 subjects and to ensure that at least 40 subjects complete the study.

3 Changes to the Protocol Defined Statistical Analysis Plan

~~There were no changes or deviations to the originally planned statistical analysis specified in the [protocol version 1.0](#)~~ The use of the Wilcoxon type test in support of the primary was removed due to limitations of that approach. Any potential supportive analysis will be considered if the ANOVA assumptions are strained. [protocol version 1.0](#) [(Dated: 06/MAR/2017)].

| | | | |
|------------------|--|---------------------|----------------------|
| Document Name | gsk-207619-reporting-and-analysis-plan.pdf | | |
| Type | Version | Document Identifier | Effective Date |
| eldo_controlled | 1.0; CURRENT; Most-Recent; Effective | 090032d580e0a875 | 06-Apr-2018 06:53:51 |
| Reason For Issue | Auto Issue | | |

4 Appendix 1:

